High schools- High on life Study protocol

29 March 2019

High schools- High on life Study protocol

The High schools- High on life intervention – aim and project organization

High schools-High on life is an intervention developed in a collaboration between the Danish Cancer Society's alcohol campaign "High on life" and the National Institute of Public Health, SDU, Denmark and evaluated by the National Institute of Public Health, SDU, Denmark. The aim of the intervention is to reduce alcohol consumption among Danish high school students and thereby contribute to a healthier alcohol culture among young people in Denmark.

The intervention will be implemented and evaluated in the school year 2019-2020

Target group: 1st year high school students in Denmark (≈16 years of age)

Background

Compared to other countries, Denmark has one of the highest levels of drunkenness among adolescents and drinking to intoxication is common even among young teenagers [1]. Among Danish high school students 28% (35% boys and 24% girls) have been binge drinking 4 or more times within the last 30 days and 20% drink above recommended high risk drinking limits of 21 units a week for men and 14 units a week for women [2].

In the short-term alcohol use in adolescence can lead to accidents, conflicts and violence [3, 4]. Excessive alcohol use in the teenage years often tracks into and through adulthood and early drinking onset increases the risk of addiction later in life [5-9]. In the long term, adolescent binge drinking has also been associated with adult physical and mental health and social consequences such as illicit drug use, school dropout and lower adulthood social class, however the existing evidence is of insufficient quality to warrant causal inferences [10, 11].

Previous primary prevention interventions have most often been targeting primary school children with the goal of abstinence or postponed debut age [12]. Educational school programs targeting primary school children have been most effective when they involved teaching skills to refuse peer pressure and drug offers and enhance social and personal competences including problem solving and decision-making skills [12-17]. However, fewer school-based interventions have been targeting High school students.

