A checklist for high schools' development/revision of the alcohol policy was developed with the aim to limit availability of alcohol, help enforcement and communicate clear attitudes to alcohol. The checklist was based on evidence from the national alcohol policies [30, 31] that have shown effect previously and interviews with principals to ensure feasibility. Most initiatives were mandatory to implement; however, some initiatives were optional because of implementation challenges or weaker evidence of impact. Headmasters will receive the checklist and be asked to tick the initiatives they intend to introduce before the new 1st year high school students begin in August 2019. Each school can decide for itself whether they also want to introduce the optional items in the checklist. Headmasters are asked to sign the adapted checklist and return it to the Danish Cancer Society to be published on the project's website. In this way, the checklist can also become a tool for leaders to promote and label their high school as a responsible institution. Headmasters are responsible for implementing and enforcing the new policy.

School educational components

-Web based education for social student committees that organize events where alcohol is sold such as parties, cafés, concerts etc. were developed, alongside with an web-based educational program for the introduction committee welcoming 1st year high school students to the high school.

The purpose of the web-based educational programs to the social student committees and intro committees is to make students aware of their responsibility for developing inclusive events, were students that do not drink also feel welcome, and the fact that they act as role models for their peers. The programs will provide information on national legislation on alcohol at high schools, marketing of alcohol, school alcohol policy, information on drinking peer pressures and social norms for adolescent alcohol use. Further, the programs provide guidance to arrange appealing social events without focusing on alcohol.

Pocket movie campaign

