- Students younger than 15 years or older than 25 years of age.

Ethics

Behavioral health prevention interventions are generally not required to notify for etic approval by the Scientific Ethics Committees{Scientific Ethics Committee, 2019 #172}. A query has been sent to the Scientific Ethics Committees for the Capital Region of Denmark (19021957).

According to the Danish Ethic Scientific Committee Act, only health science research projects must be notified to a scientific ethics committee. "Health science research project" is a concept that is defined partly in the committee act itself and partly in the executive order on the law.

Section 2 (1) of the Committee Act has the following definition of a health science research project;

§ 2. For the purposes of this Act:

1) Health science research project: A project involving experiments on live-born human subjects, human germ cells, which are intended to be used for fertilization, human fertilized eggs, embryos and fetuses, tissues, cells and human, fetus, and hereditary components or deceased. This includes clinical trials on medicinal products in humans, cf. No. 2, and clinical testing of medical devices, cf.

Data collection

The student questionnaire is based on items from other studies (e.g. The HBSC Study and the Danish National Youth Study 2014) either transferred without any revision or adapted to the high school setting [40, 41]. A few items will be developed specifically to the *High Schools- High on life* program. The student baseline alcohol questionnaire was tested among 4 high school students (3 girls and 1 boy) and followed by an interview about comprehensiveness, layout etc. The questionnaire was modified according to the students' comments and suggestions. 1st year high school students' response of the Danish National Youth Study 2019 questionnaire will serve as the baseline for the effect evaluation. The Danish National Youth Study 2019 questionnaire took around 45 minutes to answer. All 1st year high school students in intervention and the control schools should answer the follow-up questionnaire. The follow-up questionnaires will only include questions relevant to the intervention and take around 15 minutes to answer. All student questionnaires will be electronic internet-based and answered in class. Baseline data was collected from January to March 2019, while follow-up data will be collected from March to April 2020.

Outcomes

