The primary outcome is mean number of binge drinking occasions within the last 30 days. 1st year high school students will be asked "*how many times within the last 30 days have you been drinking 5 or more units of alcohol within one occasion?*". Secondary outcomes are 1) mean weekly alcohol consumption, 2) mean alcohol intake at last school party, 3) mean alcohol intake at the school during

last school party, and 4) proportion of students who think alcohol plays a too dominant part at the school (see Table 1).

Explorative outcomes: a potential positive side effect of the intervention is that a higher proportion of students feels included in the social community at school. We want to look at this among all students and further do a stratified analysis among students who do not drink or have a low alcohol intake (25% lowest quantile in mean weekly alcohol consumption at baseline among students in both interventions and control group). A potential negative side effect of the intervention is a higher alcohol intake among students in the intervention group as a response to increased focus on alcohol, making it more interesting among students in intervention group. We will also study substitute effects by analyzing whether students in the intervention group are more likely to experiment with drugs as compared to students in the control group.

Table 1: Outcomes and mediators

Variable	Question	Type	Units/categories
Primary outcome			
Binge drinking occasions	How many times within the last 30 days have you been drinking 5 or more units of alcohol within one occasion?	Continuous	Occurrences
Secondary outcomes			
Weekly alcohol consumption	How many units of alcohol have you been drinking on each day during the last week?	Continuous	Units of alcohol
Alcohol intake at last school party	How many units of alcohol did you drink at the last high school party you attended?	Continuous	Units of alcohol
Alcohol intake at the school during last school party	How many units of alcohol did you drink at the school during high school party you attended?	Continuous	Units of alcohol
Proportion of 1 st year high school students who think alcohol play a too dominant part at the school	Do you feel that alcohol plays a too dominant part at your high school (e.g.	Binary	Yes/no

*at high school parties, school bars,
introduction trips, study tours etc.)?*

Explorative outcomes

Potential positive side effects

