Proportion of 1 st year high school students who feel included in the social community at school	Are you part of the social community at your school?	Binary	Yes, always or yes, sometimes vs. Occasionally or seldom or never
Proportion of 1 st year high school students who feel included in the social community at school among students who do not drink or have a low alcohol intake (25% lowest quantile in mean weekly alcohol consumption among 1 st year students at baseline).	Are you part of the social community at your school?	Binary	Yes, always or Yes, sometimes vs. Occasionally or seldom or never

Potential negative side effect

Weekly alcohol consumption	How many units of alcohol have you been drinking on each of the days during the last week?	Continuous	Units of alcohol
Consumption of drugs.	Have you ever tried to smoke marihuana, weed, or pot?	Binary	Yes/no
	Have you ever tried other drugs than marihuana?	Binary	Yes/no

Mediators (determinants)

A clear alcohol policy	Leader/coordinator questionnaire (questions will be developed)
Alcohol policy communicated to students and parents	Leader questionnaire/coordinator (questions will be developed)
Enforcement of the alcohol policy	Leader questionnaire/coordinator (questions will be developed)

	Student questionnaire: Is it your experience that... Alcohol is sold at most social events at my high school?		
More alcohol-free social events, than events were alcohol is sold	Leader questionnaire/coordinator (questions have not been developed)		
Proportion of 1 st year high school students who overestimate the alcohol use among their peers	At your high school: How many units of alcohol do you think other young people with the same gender and school year as you drank at the last high school party you attended?	Binary	Proportion who think more than average
	Proportion who overestimate the average of the secondary outcome "Mean alcohol intake at the school during last school party"		
Proportion of 1 st year high school students who have felt a social pressure to drink	How often have you experienced any of the situations described below? I have felt a pressure to drink more than I would like to.	Binary	Often or sometimes vs. seldom or never or I never attended a party or anything like that where alcohol was served

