A blinded version of the data will be used for data analysis. Outcomes will be analyzed after the principle of intention-to-treat including all students in the arm to which they were allocated independently of whether they received (or completed) the intervention as planned. Intention-to-treat analysis will be supplemented by per protocol analysis based on the implementation of intervention components (both on school and individual level). Multi-level models will be used to account for the clustering of students in schools and school classes. General and generalized linear models will be used to study continuous and binary outcomes. If the model assumptions of the general linear model are not fulfilled, transformation of the outcome will be performed. All analyses will be adjusted for sex, parental education level, parental income and baseline level of the outcome, to increase precision. Differential effects of intervention by sex, parental educational level on the primary outcome will be investigated (explorative analyses). We hypothesize that boys may experience stronger intervention effects than girls due to higher initial level of binge drinking [43]. We had no hypotheses of the direction of socioeconomic differences in intervention effects, as previous research has been inconsistent in the direction of intervention effects [44, 45].

If the number of missing outcomes is larger than 10% and the results of the primary outcome is significant, a worst-case scenario will be performed for the primary and secondary outcomes as sensitivity analyses. The missing outcome values in the one group will be imputed with the mean value of the primary or secondary outcome of the other group and vice versa.

The primary outcome will be tested with significance level of 5%. Analyses of the pre-defined secondary outcomes will be analyzed with no p-value adjustment due to multiplicity and the interpretation of these results will be assessed in the light of multiple testing. This means that statistically significant effects will be

interpreted in the context of increased risk of type I error. No significance testing will be performed for the exploratory outcomes.

We will apply mediation analysis to test our program theory and hypothesized assumptions of changes in specific determinants will lead to change in the primary outcome.

Process evaluation

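### The 2019 baseline and 2020 follow-up surveys cover different 1st-year intakes, so the explorative low-intake stratum defined at baseline cannot give an intervention effect on either reading

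*Combined protocol and SAP*

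**What the plan says.** **Timing.** The opening section states: "The intervention will be implemented and evaluated in the school year 2019-2020". Under the alcohol policy component, headmasters choose their initiatives "before the new 1st year high school students begin in August 2019". Under Data collection, the 1st-year students' response to the 2019 national youth survey "questionnaire will serve as the baseline for the effect evaluation", and the dates are: "Baseline data was collected from January to March 2019, while follow-up data will be collected from March to April 2020". The same section has every 1st-year student in both arms answer the follow-up questionnaire.

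**Low-intake stratum.** For the social inclusion outcome, the Outcomes section proposes to "further do a stratified analysis among students who do not drink or have a low alcohol intake", defined as the "25% lowest quantile in mean weekly alcohol consumption at baseline among students in both interventions and control group". Table 1 words it as the "25% lowest quantile in mean weekly alcohol consumption among 1 st year students at baseline".

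**Covariate.** Planned statistical analysis says: "All analyses will be adjusted for sex, parental education level, parental income and baseline level of the outcome, to increase precision". It does not say whether the baseline level is a student's value or a school summary.

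**The concern.** A stratum or covariate measured at baseline normally means a value taken on the same person before exposure. Here the baseline respondents are the intake before the one that receives the intervention. By spring 2020 they would normally be in 2nd year and outside the follow-up survey. The documents describe no link between students across the surveys and no survey of the new intake before exposure.

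Two things depend on this. The first is the only planned analysis of social inclusion specifically among students who drink little or nothing, a benefit the plan names as possible. If the stratum is built from follow-up drinking instead, the arms may differ in who belongs to it, and an estimate could still be reported and interpreted without a p-value. The second is the covariate named for all analyses, whose usual student-level meaning is not available.

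**Working it through.** **Step 1: who is measured when.**

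| | Baseline | Follow-up |
|---|---|---|
| Survey window | January-March 2019 | March-April 2020 |
| Respondents | 1st-years at that time | 1st-years at that time |
| Started high school | before the window | August 2019 |

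Baseline closes in March 2019, about five months before the evaluated intake starts. Schools are common to both surveys; students are not, apart from grade repeaters.

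**Step 2: two readings of the stratum.**

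- *Own baseline intake.* Essentially no follow-up student can be classified.
- *A cut-off from the 2019 distribution, applied to 2020 intake.* This can be formed, although the plan does not state the step. Weekly consumption at follow-up is a secondary outcome that the intervention is meant to lower, so stratum membership can itself be affected by allocation.

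**Step 3: how large the second problem could be.** The documents give neither the distribution of weekly intake nor the share reporting none. Assume a share p of zero reports, exponential intake among drinkers, an unchanged control arm, and a proportional cut c in the intervention arm. The extra fraction falling below the 2019 quartile is

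s = 0.75 − (1 − p) × [0.75/(1 − p)]^(1/(1 − c)) for p below 0.25, and 0 from there on,

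and newcomers' share of the intervention-arm stratum is s/(0.25 + s). With c = 0.30:

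| p | s | Newcomer share |
|---|---|---|
| 0% | 0.0870 | 25.8% |
| 10% | 0.0564 | 18.4% |
| 20% | 0.0205 | 7.6% |
| 25% or more | 0 | 0% |

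From p = 25% the cut-off is zero units, and a proportional cut moves nobody to zero. With c = 0.10 the share runs from 8.6% at p = 0 down to 0%. With no true effect on inclusion, the contrast shifts by the newcomer share times the difference in inclusion between newcomers and the original low drinkers. That difference is also not in the documents. An assumed 10 points gives 0 to 2.6 points at c = 0.30, in either direction.

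**Step 4: the plan's sample size.** Inputs from Sample size calculation: mean 2.94, SD 2.58, ICC 0.034, 198 students per school, 30% reduction, power 0.8, level 0.05 (two-sided assumed).

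- Difference: 0.30 × 2.94 = 0.882.
- Individually randomised size: 135 per arm.
- Design effect: 1 + 197 × 0.034 = 7.698.
- 135 × 7.698 = 1,039.2 per arm; divided by 198 this is 5.25, so 6 schools per arm and 12 in all, as stated.

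No baseline covariate enters this calculation.

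**Step 5: cost of a school-level covariate.**

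- Between-school variance: 2.58² × 0.034 = 0.2263.
- Within-school part of a school mean: 2.58² × 0.966/198 = 0.0325.
- Variance of a school mean: V = 0.2588, of which 0.0325/0.2588 = 12.5% is within-school.

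With k schools per arm and correlation r between 2019 and 2020 school means, SE = √(2V(1 − r²)/k). Power is from the noncentral t distribution.

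| Schools | Unadjusted | Covariate, r = 0 | r = 0.3 | r = 0.5 |
|---|---|---|---|---|
| 16 | 89.6% (14 df) | 89.3% (13 df) | 91.9% | 95.9% |
| 12 | 77.2% (10 df) | 76.2% (9 df) | – | – |

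The documents do not give r. If uninformative, the covariate costs about 0.4 points of power with 16 schools (89.65% to 89.29%) and 1 point with 12.

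**The case against.** The best defence is that the stratum wording, above all in Table 1, can be read as a threshold taken from the 2019 1st-year distribution. That reading stands: a reader might infer that the stratum cannot be formed at all, and the documents do not support that. It does not rescue the analysis, because membership would then be decided by post-randomisation drinking.

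A second objection is that any harm may be nil. The stratum explicitly includes non-drinkers, and intake refers to a single week, so a quarter or more of students may report zero. The distortion under a proportional cut then vanishes. This also stands, and it is why no single figure can be given. It does not cover students whom the intervention moves to no drinking that week.

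Third, the analysis is explorative, no significance test is planned for it, and the all-students inclusion outcome is untouched. This limits the stakes but does not supply a workable definition.

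On the covariate, the plan does not claim a student-level value, a 2019 school summary is feasible, and the analysis uses blinded data, which limits choices driven by the result. What is missing is a detail of definition.

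**Conclusion.** The point holds, with limited reach. One explorative between-arm comparison is either empty (own baseline intake) or not an intervention effect (2019 cut-off on 2020 intake). This follows from the plan's dates and needs no numerical assumption. The size of the distortion on the second reading is unknown: 0% to about 26% newcomers for a 30% cut under the assumed exponential shape, depending on the share of zero reports.

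A reader might go on to infer that the primary analysis is compromised for want of individual baselines. The documents do not support that. Schools are randomised, the arms are compared at follow-up, adjustment is stated to be for precision, and the sample size takes no credit for it. The primary comparison is unbiased with or without the covariate.

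Nor do the documents make a 2019 school mean the required definition. It is one sound option, and any power gain rests on a correlation they do not give.

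**What to change.** 1. In the design and data collection sections, state that the evaluation is repeated cross-sectional: same schools, successive 1st-year intakes.
2. In Outcomes and Table 1, drop the low-intake stratum as an effect comparison, or keep it labelled as descriptive, with its cut-off rule written out and a statement that it does not estimate an intervention effect. Keep the all-students inclusion outcome.
3. As a secondary clarification in Planned statistical analysis, state that the baseline level of the outcome enters at school level. Options are the 2019 1st-year school mean (school proportion for binary outcomes) as one covariate, or a model of both survey years with school and school-by-year effects. Fix the choice before analysis.

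The cost is wording. The 2019 data are already collected, and the number of schools does not change. The school-mean option uses about one school-level degree of freedom, with the small power cost shown above if it proves uninformative.

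### Drug substitution is measured only as lifetime use, which mixes in use before the intervention, pulls the ratio toward 1 and costs precision

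*Combined protocol and SAP*

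**What the plan says.** Under Outcomes, among the exploratory outcomes, the plan sets out to study substitution by analysing "whether students in the intervention group are more likely to experiment with drugs as compared to students in the control group". Table 1, under the potential negative side effect, gives two binary items for this: "Have you ever tried to smoke marihuana, weed, or pot" and "Have you ever tried other drugs than marihuana". Neither has a time window, and Table 1 lists no item on recent use, frequency or date of first use. The primary outcome, by contrast, has a window: "how many times within the last 30 days have you been drinking 5 or more units of alcohol within one occasion".

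On timing, the alcohol policy section has headmasters settle their measures "before the new 1st year high school students begin in August 2019". Data collection states: "Baseline data was collected from January to March 2019, while follow-up data will be collected from March to April 2020". It adds: "All 1st year high school students in intervention and the control schools should answer the follow-up questionnaire". Planned statistical analysis adjusts every analysis for the baseline level of the outcome and says that exploratory outcomes will not be significance tested.

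**The concern.** Substitution can show itself only after the intervention starts. At follow-up in March to April 2020 the new students have been exposed for about seven to eight months, while a lifetime item covers all the years before as well. Those earlier triers are a fixed block of yes answers in both arms. They add variance and enlarge the denominator of any ratio, but carry no information about the intervention.

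This is the only drug-related harm check listed, in students of about 16. With no test planned, readers will judge it by the size of the estimate. A ratio close to 1 on the lifetime item could reassure them even if initiation had risen noticeably.

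**Working it through.** **Inputs.** The documents give no prevalence or initiation rate for any drug, so there is no drug-related figure to reproduce. Two quantities are assumed: p, the share who had tried before August 2019 (10%, 20%, 40%), and i, the share of the remaining students who first try during the school year (8% control, 12% intervention, a true risk ratio of 1.50). For absolute precision I borrow the cluster size of 198 and the intraclass correlation of 0.034 from Sample size calculation. The design effect is 1 + (198 − 1) × 0.034 = 7.698. As a check, this reproduces the plan's total: with the intervention mean rounded to 2.1 (difference 0.84, SD 2.58, two-sided 0.05, power 0.80), 149 per arm × 7.698 rounds up to 1,148, and 2 × 1,148 = 2,296.

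**Formulas.** Lifetime use = p + (1 − p)i. New use among all enrolled students = (1 − p)i. The difference between arms is (1 − p)(0.12 − 0.08) for both, so the two items estimate the same absolute excess of starters. Only the ratio and the variance differ. With equal differences, relative signal-to-noise = √(V_new / V_life), where V is the sum over arms of prevalence × (1 − prevalence). The equivalent multiple of students is V_life / V_new. This assumes the same design effect for both items.

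| p | Lifetime, control vs intervention | Lifetime RR | New use, control vs intervention | V_life | V_new | Signal-to-noise | Multiple |
|---|---|---|---|---|---|---|---|
| 10% | 0.172 vs 0.208 | 1.21 | 0.072 vs 0.108 | 0.3072 | 0.1632 | 0.73 | 1.88 |
| 20% | 0.264 vs 0.296 | 1.12 | 0.064 vs 0.096 | 0.4027 | 0.1467 | 0.60 | 2.75 |
| 40% | 0.448 vs 0.472 | 1.05 | 0.048 vs 0.072 | 0.4965 | 0.1125 | 0.48 | 4.41 |

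The new-use risk ratio is 1.50 in every row, because (1 − p) cancels.

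**Sensitivity to the assumed initiation,** true risk ratio still 1.50, p = 10%, 20%, 40%:

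- 10% vs 15%: lifetime RR 1.24, 1.14, 1.07; multiples 1.7, 2.3, 3.6.
- 5% vs 7.5%: lifetime RR 1.16, 1.08, 1.03; multiples 2.5, 4.0, 6.8.

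**Absolute precision.** Eight schools of 198 give 1,584 students per arm, or 1,584 / 7.698 = 205.8 effective students. At p = 20% with 8% vs 12%, the expected difference is 0.032. Its ratio to the standard error is 0.032 / √(0.4027 / 205.8) = 0.72 for the lifetime item and 0.032 / √(0.1467 / 205.8) = 1.20 for the new-use item. Chance imbalance in prior use alone has a standard error of √(2 × 0.20 × 0.80 / 205.8) = 3.9 percentage points, more than the 3.2 points to be seen. The randomization balances school type, size, parental education and urbanization, but not drug use.

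**Can baseline adjustment help?** Baseline answers come from students who were in 1st year in January to March 2019. The intervention is aimed at the intake of August 2019, and follow-up is described as covering 1st-year students in March to April 2020. On that wording the follow-up students have no drug answer of their own from before the intervention, and an earlier intake's school-level rate can adjust only in part.

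**The case against.** The best defence is that having ever tried a drug is a natural reading of experimenting, and that the lifetime item gives an unbiased absolute difference. Both points stand. A reader might infer that the harm estimate is biased; it is not, since the excess of starters per student is the same on either item. What is lost is precision and the usefulness of a ratio.

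The penalty is also easily overstated. Setting the lifetime item against initiation in a sample made up wholly of never-users gives multiples of 2.1, 3.5 and 7.7. No such sample exists here: a better item would go to the same students, prior triers included, and the table above uses that comparison.

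A reader might add that the item fails because it misses heavier use among earlier triers. It does miss that, but the plan asks about experimentation, so this is a limit on what can be learned rather than a mismatch with the stated aim.

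It is tempting, too, to say that prior use certainly cannot be adjusted for. The documents do not settle this. The baseline adjustment, and the subgroup defined by baseline consumption in both arms, can be read as implying individual baseline answers, although the dates point the other way. If the same students are linked, the problem for first use largely disappears.

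Finally, the outcome is exploratory and untested, it cannot alter the primary conclusion, and the plan nowhere commits to declaring that substitution is absent. That limits the importance of the point.

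**Conclusion.** The point holds as a measurement weakness in the trial's only listed check on drug substitution. Under the assumed 8% vs 12% initiation, a true risk ratio of 1.50 would appear as 1.21, 1.12 or 1.05 at prior use of 10%, 20% or 40%. The lifetime item would then need about 1.9, 2.7 or 4.4 times as many students as a new-use item to be equally informative. The direction does not depend on the assumed rates; the size does, and it grows as prior use rises or initiation falls.

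The conclusion also rests on the follow-up students having no linked drug answer from before the intervention, which the dates suggest and the authors should confirm. A better item would not make the check decisive: with 16 schools and the borrowed clustering, even new use gives a signal only 1.20 times its standard error in the middle scenario. The case for change is that it is cheap and aligns the item with the question asked.

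**What to change.** In the follow-up questionnaire, ask students who report having tried marihuana, and separately those who report other drugs, whether they first did so after starting high school. Define new use since school start, among all students, as the exploratory substitution outcome, and report it as an absolute difference and a ratio with confidence intervals. Keep lifetime use as a descriptive item.

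State whether baseline and follow-up answers come from the same individuals. If they do and can be linked, new use among baseline never-users can be reported instead.

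A 30-day item is optional and would describe current use only. The calculation here does not support it as the substitution outcome: it would miss a student who tried once in the autumn, would still count earlier users who continue, and would be less common.

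The cost is one or two short items in a questionnaire of about 15 minutes that already allows items written for this trial. There will be some recall error about when first use occurred, and no directly matching item in the 2019 survey.
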